8.1.3 Conditions Existent Before the Start of the Period of Collection (ICF Signature)

Concomitant diseases whose severity is increasing after the screening is to be captured as an AE or SAE, depending on if any seriousness criterion is met.

Therapies or surgical interventions including admissions to hospital that had been planned before the ICF signature should not be considered AEs/SAEs.

Confidentiality Statement

Data and information contained in this document are considered to constitute trade secrets and confidential commercial information, and the legal protections provided to such trade secrets and confidential information are hereby claimed under the provisions of applicable law. No part of this document may be publicly disclosed without the written consent of Philip Morris Products S.A.

8.2 Collection and Reporting of Adverse Events

8.2.1 Collection of Information

AEs should be collected mainly via face-to-face interview with the subject by the use of consistent, open, non-directive questions from the investigator(s) or designee(s) (e.g., “How have you been feeling since you were last asked?”).

Any non-serious AE occurrence during the study must be documented in the subject’s medical records in accordance with the Investigator’s normal clinical practice and on the AE page of the CRF. SAEs that occur during the study must be documented in the subject’s medical record, on the AE CRF, and on the SAE form for recording into safety database.

Information recorded for AEs/SAEs will include verbatim description, start and stop dates and times, seriousness, severity (intensity), causal relationship with IP and study procedures, action taken with IP (e.g., reduced, not changed), other action taken (e.g., treatment administered, if led to the subject’s discontinuation from the study), and outcome (e.g., resolved, stabilized).

Whenever a medically meaningful diagnosis is available to comprise a set of reported signs and/or symptoms, it should be preferentially provided as the AE or SAE term, rather than the individual signs and/or symptoms.

8.2.2 Period of Collection

AEs (including SAEs) will be collected from the time of ICF signature until the individual EOS for each participant.

Any AEs which occur during the screening period will be captured by the investigational site staff and assessed by the Investigator or designee(s) to establish relationship to study procedures.

During a 3-day Safety follow-up period new AEs/SAEs will be recorded and ongoing AEs/SAEs will be followed-up by the study site, as described in section 8.2.6.

8.2.3 Intensity of Adverse Event

The Investigator must assess the intensity of each reported AE according to the following grading scale:

Table 8 Intensity of Adverse Events

Mild:	Easily tolerated, not interfering with normal everyday activities
--------------	---

Confidentiality Statement

Data and information contained in this document are considered to constitute trade secrets and confidential commercial information, and the legal protections provided to such trade secrets and confidential information are hereby claimed under the provisions of applicable law. No part of this document may be publicly disclosed without the written consent of Philip Morris Products S.A

Moderate:	Interferes with normal everyday activities, but the subject is still able to function
Severe:	Incapacitating and requiring medical intervention

8.2.4 Relationship to Investigational Product and Relationship to Study Procedures

The Investigator must assess the causal relationship between the exposure to the IP (P4M3 Gen 2.0 and CIG) and each of the reported AEs, using the classification system and the criteria described below. The same assessment must be made separately to assess the causal relationship between the study procedures and each of the reported AEs:

Not related: The temporal relationship of the adverse event to IP administration or study procedure(s) makes a causal relationship unlikely, or concomitant medication, therapeutic interventions, or underlying conditions provide a sufficient explanation for the observed event.

Related: The temporal relationship of the adverse event to IP or study procedure(s) makes a causal relationship possible, and concomitant medication, therapeutic interventions, or underlying conditions do not provide a sufficient explanation for the observed event.

8.2.5 Expectedness

Any AE assessed as related to the IP (P4M3 or CIG) will be assessed for its expectedness. An AE will be regarded as “unexpected” if its nature or severity is not consistent with information already recorded in section 6.7 of the current Investigator’s Brochure [6].

8.2.6 Follow-up of Non-serious and Serious Adverse Events

Any non-serious AE that is ongoing at the time of Discharge or early termination will be followed-up by the Investigator during the Safety Follow-Up Period until it has been resolved, stabilized (i.e., no worsening of the condition), or an acceptable explanation has been found (e.g., a chronic condition). The follow-up of the ongoing non-serious AEs will be done via a phone call performed at the end of the Safety Follow-Up Period. If the subject is not responding at the first phone call additional two additional attempts will be made, then subject will be declared lost to follow-up.

At the end of the 3-day Safety FU Period, all ongoing non-serious AEs will have the outcome documented as “unknown” and will not be followed-up by the Investigator. At the discretion of the Investigator, the subject will be referred to his General Practitioner to have his/her ongoing AEs addressed accordingly.

Confidentiality Statement

Data and information contained in this document are considered to constitute trade secrets and confidential commercial information, and the legal protections provided to such trade secrets and confidential information are hereby claimed under the provisions of applicable law. No part of this document may be publicly disclosed without the written consent of Philip Morris Products S.A

All SAEs will be followed up by the Investigator or designee after the end of the Safety Follow-Up Period, until their resolution, stabilization (i.e., no worsening of the condition), or an acceptable explanation has been found (e.g., a chronic condition). In case the subject cannot be reached for additional information related to SAE(s), a total 3 attempts should be performed before the subject will be declared as lost to follow-up.

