Any subject who wants to attempt to quit using tobacco or nicotine containing products at any time during the study (i.e., P4M3, CIG) will be encouraged to do so and will be referred to appropriate medical services. This will not affect subject's financial compensation, and the subject will remain in the study.

- Safety follow-up period (from Discharge at Day 6 until the end of the Safety follow-up period):

After Discharge at Day 6 or from the day of early termination, subjects will enter a 3-day safety follow-up period during which AE/SAEs reported by the subjects will be collected and the follow-up of AEs/SAEs ongoing at Discharge will be conducted by the investigational site.

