4.4 Study Duration

The entire study duration per subject will be 11 to 38 days. This will include a screening period of up to 28 days prior to Admission (Day -30 to Day -3), followed by a 7-day

Confidentiality Statement

Data and information contained in this document are considered to constitute trade secrets and confidential commercial information, and the legal protections provided to such trade secrets and confidential information are hereby claimed under the provisions of applicable law. No part of this document may be publicly disclosed without the written consent of Philip Morris Products S.A.

confinement period (Day -2 to Day 5, and Discharge on Day 6), and a 3-day Safety follow-up period.

The EOS for a randomized subject is defined as the completion of the 3-day Safety follow-up period either after Discharge on Day 6, or after the date of early termination of the subject. The EOS of the entire study is the end of the Safety Follow-up Period for the last subject.

Confidentiality Statement

Data and information contained in this document are considered to constitute trade secrets and confidential commercial information, and the legal protections provided to such trade secrets and confidential information are hereby claimed under the provisions of applicable law. No part of this document may be publicly disclosed without the written consent of Philip Morris Products S.A

5 Study Population

Approximately 72 smoking healthy female or male subjects who have smoked on average at least 10 regular or menthol CIG per day for the last 4 weeks prior to Admission will be randomized (stratified by sex) into this study. Quotas will be applied to ensure that the randomized subjects contain at least 40% of both sexes (males and females) per arm.

The maximum number of CIG smoked daily is not limited. Subjects must have been smoking for at least 3 years of smoking prior to the Screening Visit. There will be no brand restrictions of CIG. Smoking status will be verified with a urinary cotinine test (cotinine ≥ 200 ng/mL).

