5.3 Lost to Follow-up

A reasonable attempt will be made to contact all participants needing to complete or resolve post-study activities (e.g., safety laboratory, physical examination, on-going AEs). Two contacts will be made via contact information provided by the subject (e.g., telephone number, cell phone number, email address), allowing 1 day between attempts for response.

The first contact attempt should take place within approximately 1-2 days of the participant's last visit to the investigational site. If contact is not possible, a follow-up letter will be sent to the participant, allowing approximately 5 business days from the time of delivery for a response. A progress note will be added in the data collection system for documentation. After a letter is sent, there should be no additional phone calls unless the participant has attempted to contact the investigational site and a return call attempt is made.

If post-study follow-up has not been resolved within approximately 5 business days following delivery confirmation or the letter is not deliverable, the participant is considered Lost to follow-up. This is documented in the progress note and outstanding AEs are updated. The date of Lost to follow-up corresponds to the date of the end of study of the subject.

The Investigator or designee(s) will declare the subject Lost to follow-up if the investigational site lost contact to the subject and the subject has reached the maximum number of study days (31 days) without making any contact.

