9.4 Safety Follow-up Period

After Discharge at Day 6, the subjects will enter a 3-day Safety follow-up period during which AE/SAEs reported by the subjects will be collected and the follow-up of AEs/SAEs will be conducted by the study investigational site as described in section 8.1.2.

Confidentiality Statement

Data and information contained in this document are considered to constitute trade secrets and confidential commercial information, and the legal protections provided to such trade secrets and confidential information are hereby claimed under the provisions of applicable law. No part of this document may be publicly disclosed without the written consent of Philip Morris Products S.A

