Data and information contained in this document are considered to constitute trade secrets and confidential commercial information, and the legal protections provided to such trade secrets and confidential information are hereby claimed under the provisions of applicable law. No part of this document may be publicly disclosed without the written consent of Philip Morris Products S.A

Abbreviations:

ABOUT = Assessment of behavioral outcomes related to tobacco and nicotine products; AE = Adverse event; B = Blood sample required; BMI = Body mass index; BoExp = Biomarker(s) of exposure; BoPH = Biomarker(s) of potential harm; CO = Carbon monoxide; COHb = Carboxyhemoglobin; CYP1A2 = Cytochrome P450 1A2; FTND = Fagerström Tobacco and Nicotine Dependence; HBV = hepatitis B virus; HCV = hepatitis C virus; HIV = Human immunodeficiency virus; HPT = Human puffing topography; SA = smoking abstinence; SAE = Serious adverse event; U = Urine sample required.

- a) Height will be recorded only at screening.
- b) Systolic and diastolic blood pressure, pulse rate, and respiratory rate.
- c) Urine will be screened for the following drugs: amphetamine type substances, barbiturates, benzodiazepines, cannabinoids, cocaine, opiates and methadone.
- d) On Day -2 (admission), after inclusion/exclusion criteria are re-checked, eligible subjects will be enrolled and perform a product test using the 2 P4M3 flavor variants (CA35 and CM35). The site staff will provide them a training before on how to use the product. After the product test, subjects not willing to use P4M3 will be discontinued.
- e) HPT recording on an ongoing basis for subjects in P4M3 arms.
- f) Provided the 28-day Screening period has not exceeded, alternate subjects have to repeat the Admission visit Day -2 of the following group to re-confirm their eligibility for randomization.
- g) If a subject is discontinued from the study after enrollment, listed early termination procedures are performed unless the subject refuses to perform the assessments or is lost to follow-up.
- h) Reporting of new AEs/SAEs by the subject and follow-up of ongoing AEs/SAEs by the site.
- i) During the safety follow-up period, only medication taken for the treatment of AEs will be recorded.

Schedule of 24-hours Urine Collection Start

	Baseline	Confinement Exposure Period				
Study Day	Day -1	Day 1	Day 2	Day 3	Day 4	Day 5
BoExp and creatinine in 24-h urine	•	•	•	•	•	•
Bio-banking samples	•	•	•	•	•	•

Abbreviations:

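### Section 8.2.6 records non-serious AEs known to be ongoing at the end of follow-up as 'unknown', the loss-to-follow-up rules contradict each other (31 against 38 days), and no post-Discharge contact is specified for subjects without an ongoing AE

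*Protocol*

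**What the plan says.** **Outcome coding.** Protocol 8.2.6 has ongoing non-serious AEs followed during the 3-day period until they are resolved, stable or explained. On the means of contact it says: "The follow-up of the ongoing non-serious AEs will be done via a phone call performed at the end of the Safety Follow-Up Period". A subject who does not answer is tried twice more and then declared lost to follow-up. The next paragraph says that at the end of the period "all ongoing non-serious AEs will have the outcome documented as" 'unknown', with no further follow-up by the investigator. SAEs are treated differently and are followed beyond the period.

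**Loss to follow-up.** Protocol 5.3, repeated in SAP 4.5.4, makes the declaration when the site has lost contact and "the subject has reached the maximum number of study days (31 days) without making any contact". Protocol 4.4, repeated in SAP 4.4, says: "The entire study duration per subject will be 11 to 38 days".

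**New AEs after Discharge.** Protocol 4.1 describes a 3-day period "during which AE/SAEs reported by the subjects will be collected", and 9.4 says the same. Footnote h of Appendix A reads: "Reporting of new AEs/SAEs by the subject and follow-up of ongoing AEs/SAEs by the site". Section 8.2.2 says: "During a 3-day Safety follow-up period new AEs/SAEs will be recorded and ongoing AEs/SAEs will be followed-up by the study site". Section 9.4 refers the reader to 8.1.2 for the procedure.

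**The concern.** An end-of-period call is made to learn whether an event is still present. If the answer is yes, the rule discards it. Outcome is one of the items to be recorded for each AE (Protocol 8.2.1, SAP 9.6.5.1), and under this rule the field cannot by itself show which non-serious events persisted.

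The loss-to-follow-up text gives sites two procedures and a day limit that is inconsistent with the study's length, so two sites could handle the same subject differently and both be following the protocol.

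AEs are the main assessment of safety. The SAP tabulates them by arm and by safety period, with follow-up as a separate period. A collection method that is left open for some subjects in that period is worth settling before data are collected, because a question not asked on Days 7 to 9 cannot be asked later with the same value.

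**Working it through.** **1. What the outcome field can hold.** Apply 8.2.6 to a non-serious AE that was ongoing at Discharge, according to what the final call finds:

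| Finding at end of follow-up | Outcome recorded under 8.2.6 |
|---|---|
| Resolved | resolved |
| Present and stable | 'unknown' under the all-ongoing rule, although stabilized is named as an outcome in 8.2.1 and as an end point in 8.2.6 |
| Present and not stable | 'unknown' |
| Subject not reached after three attempts | 'unknown', plus lost to follow-up |

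Three different states share one code, and for two of them the status is known.

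**2. Study length.** The inputs are Protocol 4.4 and the Appendix A day numbering, which has no Day 0.
- Screening, Day -30 to Day -3: 28 days at most, 1 day at least.
- Confinement, Day -2 to Day 5: 2 + 5 = 7 days.
- Safety follow-up, Days 7 to 9: 3 days.
- Maximum: 28 + 7 + 3 = 38. Minimum: 1 + 7 + 3 = 11. Both stated figures reproduce exactly. Counting Discharge Day 6 as its own day gives 39 and 12.
- The 31-day maximum does not reproduce: 38 - 31 = 7 days short, or 8 if Day 6 is counted. It happens to equal 28 + 3, the total without confinement, but the documents do not say where it comes from.

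**3. Where day 31 could fall.** No start is stated. If the count began at the Screening visit (an assumption), a subject screened on Day -30 would reach day 31 on Day 1 (30 + 1). One screened on Day -23 would reach it on Day 8 (23 + 8), and one screened on Day -22 on Day 9 (22 + 9). On that count the limit precedes the end of follow-up only for subjects screened on Day -23 or earlier.

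**4. The two contact procedures, for a subject discharged on Day 6.**
- Section 5.3: first contact about Day 7 or 8, a second after a 1-day gap, then a letter and about 5 business days from delivery. With the second contact on Day 8 and same-day delivery, a delivered letter runs to Day 13 at the earliest (8 + 5).
- Section 8.2.6: first call at the end of follow-up (Day 9), then two more attempts and no letter.
- Section 5.3 also makes the lost-to-follow-up date the subject's end of study, whereas 4.4 sets it at completion of the 3-day period. AE collection runs to the individual end of study (8.2.2), so its closing date depends on which section is followed.

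**5. Cross-reference.** Section 8.1.2 defines an SAE and contains no follow-up procedure. Sections 8.2.2 and 8.6 send the reader to 8.2.6 for the same purpose.

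**6. Contact for subjects with nothing ongoing.** The 8.2.6 call is described for ongoing non-serious AEs. Section 5.3 covers participants with something left to complete or resolve. Appendix A marks AE recording on Days 7 to 9 for everyone, but footnote h describes new events as coming from the subject. No section states a call or question for a subject discharged with no open event.

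**The case against.** Much can be said in mitigation, and most of it limits the point without removing it.

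- The 'unknown' code applies only to non-serious AEs still ongoing at the end of follow-up. A subject who was never reached is separately declared lost to follow-up, and SAP 9.2 lists disposition, so part of the distinction can be recovered by cross-reference. That stands. It does not restore whether a confirmed event was stable, and it leaves the outcome field wrong for confirmed ongoing events.
- The SAP describes no table by AE outcome, and safety is descriptive with no inference. That also stands: the effect is on the outcome data and listings.
- The 31-day rule also requires lost contact. A subject in confinement is seen daily, so reaching day 31 during the exposure period triggers nothing by itself. The contradiction in the text remains.
- A reader might infer that new AEs are actively sought only in subjects who already have one, biasing the comparison between arms. The documents do not support this. Section 8.2.6 gives the call's purpose as following ongoing events and does not say that new events are elicited. Read literally, footnote h applies the same self-report to everyone. Section 8.2.1 makes open questioning the main method, and an event reported by a subject need not be unprompted. The SAP follow-up period also includes the Day 6 recording made in all subjects still confined, and after Discharge any tobacco or nicotine product may be used (Protocol 6.2.5), which weakens any link between Day 7 to 9 events and arm. What can be said is that the contact method for these subjects is unspecified.

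**Conclusion.** Two things are wrong as written. First, the outcome rule in 8.2.6 replaces a known status with 'unknown' for every non-serious AE confirmed present at the end of follow-up. Second, the loss-to-follow-up text conflicts with itself and with the study's length: 31 days against 38, two contacts plus a letter against three calls, and a wrong cross-reference in 9.4.

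The absence of a specified contact for subjects without an ongoing AE is a gap that can be closed cheaply. It is not a demonstrated bias between arms.

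The 7-day shortfall follows from the documents' own figures. Any statement about where day 31 falls depends on counting from Screening, which is an assumption. How many AEs would be miscoded or missed cannot be computed, since no AE rates are given. It would go too far to infer that AE outcomes in general are wrong, because SAEs and resolved events are unaffected. The primary biomarker analysis does not depend on any of this.

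**What to change.** 1. In 8.2.6 and the CRF, record non-serious AEs confirmed present at the final call as 'ongoing/not resolved', and keep 'unknown' for events whose status could not be obtained. Cost: one outcome code and a sentence.
2. Reconcile 5.3, 8.2.6 and SAP 4.5.4 into one contact procedure. Give the day limit a stated start and make it consistent with the 38 days in Protocol 4.4 and SAP 4.4, and align the end-of-study date for lost subjects. Change the 9.4 reference from 8.1.2 to 8.2.6. Cost: wording only.
3. As an improvement, state in 8.2.6, 9.4 and Appendix A that every subject in the Safety Set is asked the open question of 8.2.1 at the end of follow-up, so that collection is uniform across arms. Cost: short calls by existing site staff to the 72 randomized subjects and to those enrolled but not randomized, who also enter the 3-day period.

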8.3 Reporting of Serious Adverse Events

Any SAE observed during the period of collection in this study must be reported within 24 hours of first awareness to Sponsor, via email, having the SAE form attached.

Follow-up information should be reported on a new SAE report form, marked as a follow-up report, and submitted to Sponsor according to the same timelines as described above. The follow-up SAE report form must include the minimum information required for form completion and only changed/new information needs to be specified. Information provided in the follow-up SAE report form supersedes any information that was initially reported.

The Investigator or designee is responsible for submitting the relevant reports of SAEs that occur during the study to the IEC, according to local regulations.

8.4 Reporting of Other Abnormal Findings

The other abnormal findings discovered during different clinical assessments (e.g., ECG, spirometry, vital signs, body weight) should be evaluated for the clinical significance by the Investigator/designee based on his/her medical judgement. All abnormal clinically significant test results or clinical examination findings can, at the discretion of the Investigator, be reported as AEs and handled according to the directions from section 8.2.

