5.2 Discontinuation of Subjects from the Study

Discontinued subjects (i.e., enrolled subjects that do not complete the study) will include both subjects who withdraw from the study (subject's decision) or subjects who are discontinued from the study by the decision of the Investigator.

Confidentiality Statement

Data and information contained in this document are considered to constitute trade secrets and confidential commercial information, and the legal protections provided to such trade secrets and confidential information are hereby claimed under the provisions of applicable law. No part of this document may be publicly disclosed without the written consent of Philip Morris Products S.A

Subjects will be informed that they are free to withdraw from the study at any time. Subjects should be questioned for the reason of withdrawal from the study, although they are not obliged to disclose it.

If the subject withdraws from the study, this information will be fully documented by the PI or designee including:

- The early termination procedures for safety assessments will be performed as defined in section 9.5, unless the subject refuses to perform the assessments.
- The samples collected up to the time of withdrawal that have been analyzed and data collected up to the time of withdrawal will be used in the analysis and report. If the subject refuses that non-analyzed samples and data will be used, he/she needs to document his disagreement in writing.

Subjects must be discontinued from the study for any of the following reasons:

- Withdrawal of informed consent
- Non-adherence to allocated product or to smoking abstinence
- Subject becomes an employee of the investigational site, or any other parties involved in the study, or their first-degree relatives (parent, sibling, and child)
- Any AE or condition (including clinically significant changes in a laboratory parameter) which at the discretion of the Investigator no longer justifies the subject's participation in this study
- Positive pregnancy test
- Discontinuation considered to be in the best interest of the subject or the other subjects, as judged by the Investigator
- Subject unwilling to use the product during the entire study duration after having done the product test.
- An alternate subject that has completed the Screening period and has not been randomized.

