7.4 Clinical and Other Assessments

The results of the clinical assessments described in this section will be recorded in the CRF.

Any clinically relevant medical condition detected during Screening visit assessments has to be documented as a concomitant disease. This also applies to clinically relevant findings in laboratory values, vital signs, spirometry, and ECGs detected during Screening visit assessments. Any untoward medical occurrence in a subject detected during the study which was not present at Screening visit must be documented as an AE. Worsening of a pre-existing condition from Screening visit onwards will also be documented as an AE.

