7.4.5 Vital Signs

Vital signs will include systolic and diastolic blood pressure, respiratory rate and pulse rate.

All parameters will be recorded in supine position after the subject has rested for at least 5 minutes. Subjects should have abstained from using any TNP for at least 15 minutes prior to Vital signs assessment.

For those results outside of the normal range, the Investigator will determine appropriate follow-up including reporting of any AEs.

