8.1 Definitions

8.1.1 Adverse Events

An adverse event (AE) is defined as any health-related event which is adverse or unfavorable and which either starts after ICF signature or represents a worsening of a health-related condition that existed at the time of that signature. Careful medical judgment is required to establish whether a clinical finding (including an abnormal laboratory result) is a true AE or just a manifestation of a preexisting health-related condition. An AE may or may not have a causal relationship with the study procedures or with the use of investigational product.

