**Table 14 Clinical Laboratory Parameters Safety Panel**

Hematology	Clinical Chemistry	Urine Analysis
- Hematocrit	- Albumin	- pH
- Hemoglobin	- Total protein	- Bilirubin
- Mean corpuscular hemoglobin	- Alkaline phosphatase	- Glucose
- Mean corpuscular hemoglobin concentration	- Alanine aminotransferase	- Nitrite
- Mean corpuscular volume	- Aspartate aminotransferase	- Red blood cell traces
- Platelet count	- Blood urea nitrogen	- Protein
- Red blood cell count	- Creatinine	- Specific gravity
- White blood cell (WBC) count	- Gamma-glutamyl transferase	
- Differential WBC count:	- Fasting glucose*	
• Neutrophils	- Lactate dehydrogenase	
• Basophils	- Potassium	
• Eosinophils	- Sodium	
• Lymphocytes	- Total bilirubin	
• Monocytes	- Direct bilirubin	
	- Total cholesterol	
	- Triglycerides	

Descriptive statistics for actual values and changes from baseline will be produced for the clinical chemistry, hematology, and urinalysis safety panel, for the SAF.

All laboratory data will be listed for all subjects.

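### Protocol 8.4 makes AE recording of clinically significant findings optional and gives no criterion, which conflicts with the natural reading of 7.4 and goes beyond the judgment allowed in 8.1.1

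*Protocol*

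**What the plan says.** Protocol 8.4 deals with abnormal findings from assessments such as ECG, spirometry, vital signs and body weight. The investigator first decides on clinical significance. The section then adds: "All abnormal clinically significant test results or clinical examination findings can, at the discretion of the Investigator, be reported as AEs".

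Protocol 7.4 says: "Any untoward medical occurrence in a subject detected during the study which was not present at Screening visit must be documented as an AE". It also requires worsening of a pre-existing condition after Screening to be recorded as an AE. The sentence in 7.4 that names types of test concerns Screening findings, which are recorded as concomitant disease: "This also applies to clinically relevant findings in laboratory values, vital signs, spirometry, and ECGs detected during Screening visit assessments".

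Protocol 8.1.1 defines an AE as "any health-related event which is adverse or unfavorable and which either starts after ICF signature", or as a worsening of a condition that already existed. On test results it says: "Careful medical judgment is required to establish whether a clinical finding (including an abnormal laboratory result) is a true AE". The alternative it names is a mere expression of a pre-existing condition.

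For vital signs, Protocol 7.4.5 says: "For those results outside of the normal range, the Investigator will determine appropriate follow-up including reporting of any AEs". Sections 7.4.3 (physical examination), 7.4.6 (spirometry) and 7.4.7 (ECG) use the same wording.

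The study is open-label (Protocol 6.4). AE data are the main safety assessment, and no inferential safety analysis is planned (Protocol 12.6.2; SAP 9.6.3.2 and 9.6.5.1).

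**The concern.** An investigator who follows 8.4 may accept that a new finding is abnormal and clinically significant and still not record it as an AE. An investigator who follows 7.4 would normally have to record it. Both are complying with the protocol, so the same finding can be in the AE tables for one subject and absent for another.

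The person who decides knows the arm. The blinding arrangements (Protocol 12.9.2, SAP 4.6.2) cover biomarker data for the statisticians and the clinical scientist and, in the SAP, the classification of protocol deviations. They do not reach AE ascertainment. A discretion without a criterion can therefore be used differently in the P4M3, CIG and SA arms, even in good faith. At stake is how far the arms' AE rates can be compared where the AEs come from tests or examinations.

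**Working it through.** The plan states no figure on this point, so there is nothing to reproduce. The check sets the texts side by side and then sizes the effect of one decision.

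**1. The texts**

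| Protocol section | What it covers | Is AE recording required? | Room for judgment |
|---|---|---|---|
| 7.4 | Any untoward occurrence that is new since Screening; worsening of an existing condition | Yes | None stated |
| 8.1.1 | Any clinical finding, abnormal laboratory results included | Follows from the definition | True AE, or an expression of an existing condition |
| 7.4.3, 7.4.5, 7.4.6, 7.4.7 | Results outside the normal range | Left to the investigator | No criterion |
| 8.4 | Findings already judged abnormal and clinically significant | Optional | No criterion |

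The judgment in 8.1.1 has a defined question. The one in 8.4 has none, comes after clinical significance has been accepted, and applies to all such findings, new ones included. Section 8.2.1 requires documentation only once something counts as an AE, so it does not settle the matter. Nor does the SAP give a rule.

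**2. What the tables show if no AE is recorded**

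- Laboratory (SAP 9.6.5.3.1): "Descriptive statistics for actual values and changes from baseline will be produced for the clinical chemistry, hematology, and urinalysis safety panel". Vital signs (9.6.5.3.5) and spirometry (9.6.5.3.6) are treated the same way. Minimum and maximum are among the statistics (SAP 9.1.3), and all values are listed. No post-baseline table by clinical significance is planned for these three.
- ECG (SAP 9.6.5.3.7): also tabulated by clinical significance at each visit. A clinically significant ECG finding would be visible there, possibly with no matching AE.

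**3. Size of one decision**

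Inputs: 18 randomized subjects per arm and 36 in the combined P4M3 arms (Protocol 4.1 and 12.9.4); the SAP's threshold for a common AE, a preferred term with incidence of at least 5% in any arm (SAP 9.6.5.1).

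- One arm, for a subject whose only event is the finding: 1/18 = 0.0556, or 5.6 percentage points of AE incidence.
- Combined P4M3 arms, same subject: 1/36 = 0.0278, or 2.8 points.
- Common-AE table: 5.6% is at least 5%, so one recorded case in an arm of 18 is enough to enter a preferred term. If nobody else has that term, the one decision puts it in the table or keeps it out.

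**The case against.** The strongest reply is that 7.4 does not literally cover post-screening test results. Its sentence naming laboratory values, vital signs, spirometry and ECG is confined to Screening, and its mandatory sentence speaks only of untoward occurrences. On this view a test abnormality becomes an AE only after the judgment described in 8.1.1, and 8.4 restates that judgment. Sections 7.4.3 and 7.4.5 to 7.4.7 show the same reliance on the investigator.

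The point about wording stands. A reader might infer that 7.4 expressly orders AE recording of every clinically significant test result, and the text does not say so. But a new finding accepted as clinically significant is naturally an untoward occurrence, and the discretion in 8.4 is not tied to the question in 8.1.1. The out-of-range wording in the 7.4 subsections has no criterion either, so it does not reconcile the two.

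Other limits also stand:

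- A reader might infer that every withheld finding moves an arm's incidence by 5.6 points. It does so only if the subject has no other AE. Two withheld findings make 2/18 = 11.1 points only if they occur in two such subjects.
- A reader might infer that such findings vanish from the report. The listings, the minima and maxima and the ECG table still show them.
- Under Protocol 5.2 a subject must be discontinued for "Any AE or condition (including clinically significant changes in a laboratory parameter) which at the discretion of the Investigator" rules out continuing, and 8.4 as written would still not require an AE. The reason for discontinuation is documented (Protocol 6.2.6) and reported (SAP 9.2), however, so the case would not be hidden.
- Safety laboratory tests, ECG and spirometry have one scheduled assessment after exposure, on Day 6, so there are few occasions for such findings.

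**Conclusion.** The point holds. Section 8.4 adds a second, criterion-free discretion after clinical significance has been accepted. It conflicts with the natural reading of 7.4, goes beyond the judgment in 8.1.1, and is not reconciled elsewhere in the protocol or SAP. It lets an unblinded investigator leave clinically significant findings out of the data that carry the main safety assessment.

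The 5.6 and 2.8 points are per subject and assume that all randomized subjects are in the Safety Set in their randomized arm and that the subject has no other AE. The documents give no expected number of such findings, so the total effect cannot be estimated.

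The reach is limited to AEs that arise from tests or examinations. Section 8.4 does not make AEs elicited at interview or SAE reporting optional, and the biomarker analyses, including the primary objective, are unaffected. The documents show that differential recording is possible. They give no evidence that it will happen.

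**What to change.** In Protocol 8.4, replace the optional clause with a rule: abnormal findings judged clinically significant that are new or worsened since Screening must be recorded as AEs, under the diagnosis where one is available (8.2.1), unless judged under 8.1.1 to be only an expression of a pre-existing condition that has not worsened. Add a cross-reference to this rule in 7.4.3, 7.4.5, 7.4.6 and 7.4.7, so that one criterion applies to all assessments and all arms.

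This removes the second discretion. The unblinded investigator still judges clinical significance, so some dependence on that person remains, and the change should not be presented as removing it.

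The cost is one revised sentence, four cross-references and possibly a few more AE records. No assessment, visit or analysis is added.
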